6.12.3.2. Systemic Hypersensitivity Reaction

The number and proportion of patients experiencing treatment-emergent potential systemic hypersensitivity reactions will be summarized and compared by treatment group using Fisher's exact test. The following MedDRA Standardised MedDRA Queries (SMQ) will be used to identify potential systemic hypersensitivity reactions from all TEAEs:

- Anaphylactic reaction (SMQ). Besides using the narrow and broad terms designated within the SMQ, the following search algorithm will also be implemented as another approach to determine if a patient had an anaphylactic reaction: if a patient (had at least 1 event in Category A) or (had at least 1 event that is in category B and also had at least 1 event that is in category C) or (had at least 1 event that is in category D and [also had at least 1 event in category B or at least 1 event in category C])

- Angioedema (SMQ)
- Hypersensitivity (SMQ)

Specifically, need to perform the following: (1) any narrow or algorithmic term from any 1 of the 3 SMQs indicated above (that is, combined search across narrow and algorithmic portions of all 3 SMQs); (2) any narrow scope term within each SMQ, separately (that is, narrow SMQ search); (3) any term within each SMQ, separately (that is, broad SMQ search); (4) narrow scope term search within each SMQ, report the PT nested within each SMQ.

A similar summary will be provided for the TEAE related to study drug judged by investigator.

Note that an individual patient may contribute multiple events. Also, a single event may satisfy multiple SMQs, in which case the event contributes to every applicable SMQ.

6.12.3.3. Infusion Site Reaction

The infusion site reactions will be searched by MedDRA PTs from all TEAEs. The number and percentage of patients experiencing treatment-emergent infusion site reaction will be summarized and compared by treatment group using Fisher's exact test.

For infusion site reactions identified by MedDRA PTs, the presence and severity of erythema, induration, pain, pruritus and edema (collected on the eCRF Infusion Site Reaction Questionnaire form) will be summarized for each treatment. Also, by anatomical location of the reaction for overall infusion site reaction will be summarized. There will be no statistical comparison between treatments.

6.12.3.4. Hepatobiliary Events

6.12.3.4.1. *Treatment-Emergent Potential Hepatic Disorder*

The percentages of patients with treatment-emergent drug-related hepatic disorder events will be summarized and compared by treatment group using MedDRA PT nested within each SMQ ordered by decreasing frequency. The following SMQs based on MedDRA will be used to identify potential hepatic disorders:

- broad and narrow terms in the Liver related investigations, signs and symptoms SMQ (20000008)
- broad and narrow terms in the Cholestasis and jaundice of hepatic origin SMQ (20000009)
- broad and narrow terms in the Hepatitis non-infections SMQ (20000010)
- broad and narrow terms in the Hepatic failure, fibrosis and cirrhosis and other liver damage SMQ (20000013)
- narrow terms in the Liver-related coagulation and bleeding disturbances SMQ (20000015)

The percentage of patients with any 1 of the terms will be summarized in addition to the percentages for each MedDRA PT. The percentages of patients with potentially drug-related

hepatic disorders that led to permanent study treatment discontinuation will be summarized similarly.

6.12.3.4.2. Liver Enzyme Lab Values

The liver enzyme measures (alanine aminotransferase [ALT], aspartate aminotransferase [AST], alkaline phosphatase [ALP], direct bilirubin, total bilirubin) will be summarized by treatment group. Post-baseline value and the change from baseline (last nonmissing value before randomization) to post-baseline value at Week 16 visit (planned test) will be summarized for patients who have both a baseline and at least 1 postbaseline result, and compared between treatment groups by using ANCOVA model with the term of treatment and baseline value of the response variable. All analyses will be provided in both SI and CN units.

The last nonmissing observation at or prior to Week 26 (including early discontinuation visits) will also be analyzed by an ANCOVA model with the term of treatment, baseline value of response variable.

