5.3.1. Safety Follow-up

Safety follow-up visit guidelines are as follows (see Section 2, [Table ITRO.1](#).):

- Patients who discontinue from the study during the lead-in period (prior to randomization), only need to complete an early discontinuation visit.
- Patients who discontinue from IP early will be encouraged to remain in the study and complete all remaining visits per the Schedule of Activities, including Visit 801.
- Patients who discontinue from the study early (regardless of whether they discontinue IP at the same time or have discontinued IP at an earlier visit), should complete an early discontinuation visit followed by the safety follow-up visit as per the Schedule of Activities.
- Patients who finish Visit 13 without early discontinuation of IP should complete a safety follow-up visit (Visit 801) 4 weeks after Visit 13.

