7.2.1.5. Transitioning off Study Prandial Insulin Therapy

Patients will give their last bolus dose of study insulin (LY900014 or Humalog) at Visit 13 with the MMTT or at early discontinuation. No special instructions are necessary for patients who were randomized to either LY900014 or Humalog. After completion of study treatment, patients will restart the rapid-acting insulin analog used prior to study entry via CSII and their pumps settings will be reset to those used at randomization.

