9.4.6.1. Hepatic Safety Monitoring

If a study patient experiences elevated ALT ≥ 3 X ULN, ALP ≥ 2 X ULN, or elevated TBL ≥ 2 X ULN, liver testing ([Appendix 4](#)) should be repeated within 3 to 5 days including ALT, AST, ALP, TBL, direct bilirubin, gamma-glutamyl transferase, and creatine kinase to confirm the abnormality and to determine if it is increasing or decreasing. If the abnormality persists or worsens, clinical and laboratory monitoring should be initiated by the investigator and in consultation with the study medical monitor. Monitoring of ALT, AST, TBL, and ALP should continue until levels normalize or return to approximate baseline levels.

Hepatic Safety Data Collection

Additional safety data should be collected via the eCRF if 1 or more of the following conditions occur:

- Elevation of serum ALT to ≥ 5 X ULN on 2 or more consecutive blood tests
- Elevation of serum TBL to ≥ 2 X ULN (except for cases of known Gilbert's syndrome)
- Elevation of serum ALP to ≥ 2 X ULN on 2 or more consecutive blood tests
- Patient discontinued from treatment due to a hepatic event or abnormality of liver tests
- Hepatic event considered to be a SAE

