5.1. Summary of Study Design

Study I8B-MC-ITRO (ITRO) is a Phase 3, prospective, randomized, outpatient, multinational, multicenter, 2-treatment group, parallel, active-controlled, double-blind study conducted in patients with type 1 diabetes (T1D) currently using continuous subcutaneous insulin infusion (CSII) therapy. Patients will be randomized to receive LY900014 or Humalog as both basal and bolus insulin and will administer bolus doses 0 to 2 minutes prior to meal (pre-meal). The study is designed to demonstrate noninferiority of LY900014 when compared with Humalog in change in HbA1c from baseline to Week 16, when both are used via CSII and bolus doses are given prior to the start of the meal. The study periods include 1-week screening, 2-week lead-in, 16-week treatment, and a 4-week safety follow-up. [Figure ITRO 5.1](#) illustrates the study design.

Patients treated with a rapid-acting insulin analog—insulin lispro, insulin aspart, or insulin glulisine via CSII—will be eligible for inclusion in the trial. All patients will use Humalog during the lead-in period. Those treated with either insulin aspart or insulin glulisine at screening will be transferred to Humalog at Visit 2. At Visit 4, patients will be randomized to either LY900014 or Humalog with bolus doses given immediately prior to each meal. Specific elements of this study design will include collection of 10-point self-monitored blood glucose (BG), blinded CGM sessions, and Mixed Meal Tolerance Testing.

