Health outcomes: ITSQ, EQ-5D-5L, EQ-VAS	All Randomized Patients with a baseline and a post-baseline observation	Last of Visits 2-4 prior to initiation of IP	Last of Visits 5-13 prior to discontinuation of IP
Safety Laboratory Tests (chemistry, hematology) – continuous analysis	All Patients in the Safety Population with a baseline and a post-baseline observation	Visit 1	Visit 13 (planned) AND last of Visits 5-13 (planned including early discontinuation visits) regardless of IP use
Safety Laboratory Tests (chemistry, hematology) – categorical analysis	All Patients in the Safety Population with a normal baseline (with respect to the direction being analyzed) and a post-baseline observation	Visits 1-4 (including unplanned tests)	Visits 5-13 (including unplanned tests) regardless of IP use
TEAEs	All Patients in the Safety Population	Prior to first dose of randomized IP (or Visit 4 date if the dose date is missing) but after the first dose of open-label insulin lispro in the Lead-in Period	From first dose of randomized IP to last dose of randomized IP AND From first dose of randomized IP to Visit 801
Hypoglycemia events	Safety Population	All Visits 2-4	All Visits 5-13 prior to discontinuation of IP
Unplanned infusion set changes	Safety Population	All Visits 2-4	All Visits 5-13 prior to discontinuation of IP
Weight and vital signs	All Patients in the Safety Population	Last of Visits 2-4	Visits 5-13 prior to discontinuation of IP

	with a baseline and a post-baseline observation		
Anti-insulin lispro antibodies	Safety Population	Visit 4	Visits 5-801 regardless of IP use

Abbreviations: 1,5-AG = 1,5-Anhydroglucitol; AIT = active insulin time; ANCOVA = analysis of covariance; CR = carbohydrate ratio; EQ-5D-5L = European Quality of Life – 5 Dimensions 5 Level; EQ-VAS = EuroQol visual analogue scale; HbA1c = hemoglobin A1c; IP = investigational product; ISF = insulin sensitivity factor; ITSQ = Insulin Treatment Satisfaction Questionnaire; ITT = intention-to-treat; LOCF – last-observation-carried forward; MMTT = mixed meal tolerance test; MMRM = mixed-effect model repeated measures; PPG = postprandial glucose; SMBG = self-monitored blood glucose; TEAE = treatment-emergent adverse event.

¹ If the percentage of the patients with missing MMTT data at baseline is higher than 15%, a constrained longitudinal data analysis model (Liu et al. 2009; Lu 2010) will be used instead. See Section 6.11.2.

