6.12.3.4.3. Treatment-Emergent Elevation of Liver Enzyme Lab Values

The percentages of patients with the following elevations in hepatic laboratory tests at any time during the treatment period (0 to 16 weeks) will be summarized between treatment groups:

- The percentages of patients with post-baseline ALT measurement ≥ 3 times (3X), 5 times (5X), and 10 times (10X) the Covance upper limit of normal (ULN) will be summarized for all patients with a post-baseline value by the following baseline categories: $\leq 1X$, $> 1X$ to $< 3X$, $\geq 3X$, missing.
- The percentages of patients with post-baseline AST measurement greater than or equal to 3 3X, 5X, and 10X the Covance ULN will be summarized for all patients with a post-baseline value by the following baseline categories: $\leq 1X$, $> 1X$ to $< 3X$, $\geq 3X$, missing.
- The percentages of patients with post-baseline total bilirubin measurement ≥ 2 times (2X) the Covance ULN will be summarized for all patients with a post-baseline value by the following baseline categories: $\leq 1X$, $> 1X$ to $< 2X$, $\geq 2X$, missing.

Baseline will be the maximum observation in the baseline period including the lead-in period. The maximum value will be the maximum value from the treatment period. Planned and unplanned tests will be included.

Graphical profiles of ALT, AST, total bilirubin, and ALP will be provided for patients with an ALT or AST $\geq 3X$ ULN or total bilirubin $\geq 2X$ ULN during the treatment period. A listing for these patients will also be provided, including the actual measurement of ALT, AST, ALP, and total bilirubin, the corresponding reference high limits, demographics, disposition, drug exposure and AEs. The review for these patients includes an assessment of the proximity of any ALT or AST elevation to any total bilirubin elevation, ALP levels, other potential causes, and the temporal association with events such as nausea, vomiting, anorexia, abdominal pain, or fatigue.

All patient data, regardless of whether on IP, will be used for the above analyses related to hepatobiliary events.

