6.12.4. Clinical Laboratory Evaluation

The data from safety laboratory measures will be summarized at Week 16 where the lab test is planned to be collected. Postbaseline and change from baseline to postbaseline for laboratory tests will be summarized for patients who have both baseline and at least 1 post-baseline result and compared between treatment groups by using ANCOVA model with the term of treatment and baseline value of the response variable. Analyses will be provided in both SI and CN units.

The last nonmissing observation at or prior to Week 16 (planned tests including early termination) will also be analyzed by an ANCOVA model with the term of treatment, baseline value of the response variable.

The percentages of patients with treatment-emergent abnormal, high, or low laboratory results at any time during the treatment period (0 to 16 weeks) will be summarized for patients who have both baseline and at least 1 post-baseline result and compared between treatment groups using Fisher's exact tests. A treatment-emergent abnormal result is defined as a change from normal at all baseline visits to abnormal at any time during the treatment period. A treatment-emergent high result is defined as a change from a value less than or equal to the high limit at all baseline visits to a value greater than the high limit at any time during the treatment period. A treatment-emergent low result is defined as a change from a value greater than or equal to the low limit at all baseline visits to a value less than the low limit at any time during the treatment period.

Planned and unplanned measurements will be included. Covance reference ranges will generally be used to define the low and high limits. Only patients who have normal baseline values for the analysis being performed will be included in the analysis for treatment-emergence.

Liver enzymes measures will not be included in the above analyses as different analyses will be used as described in Section 6.12.3.4.2 and Section 6.12.3.4.3.

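### The supplementary last-observation analysis of liver enzymes is cut off at Week 26, a time point this trial does not have, and its rule does not restrict it to planned tests

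*SAP*

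**What the plan says.** SAP 6.12.3.4.2 plans two continuous analyses of ALT, AST, ALP and direct and total bilirubin. The first is an ANCOVA of the value at the Week 16 visit, explicitly the planned test. The second is supplementary: "The last nonmissing observation at or prior to Week 26 (including early discontinuation visits) will also be analyzed by an ANCOVA model".

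For the remaining laboratory tests, SAP 6.12.4 has the parallel sentence with a different limit: "The last nonmissing observation at or prior to Week 16 (planned tests including early termination) will also be analyzed by an ANCOVA model". That section then takes liver enzymes out of its own analyses and points to 6.12.3.4.2 and 6.12.3.4.3.

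Table ITRO 6.2 (SAP 6.1) gives the post-baseline observations for continuous analysis of chemistry and hematology as "Visit 13 (planned) AND last of Visits 5-13 (planned including early discontinuation visits) regardless of IP use". Protocol 10.3.1 confines safety laboratory analyses to the planned treatment period, on or off study drug.

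The calendar is stated in SAP 5.1: "The study periods include 1-week screening, 2-week lead-in, 16-week treatment, and a 4-week safety follow-up". Under protocol 5.3.1, patients who finish Visit 13 on study drug "should complete a safety follow-up visit (Visit 801) 4 weeks after Visit 13".

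**The concern.** A pre-specified safety analysis carries a cut-off that matches no time point in the trial, and its selection rule differs from the two nearest rules. A programmer must then choose between the sentence as printed and Table ITRO 6.2.

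The choice can matter for the patients of hepatic interest. Protocol 9.4.6.1 says that after ALT of at least 3 times, ALP of at least 2 times or total bilirubin of at least 2 times the upper limit of normal, liver tests "should be repeated within 3 to 5 days including ALT, AST, ALP, TBL, direct bilirubin" and other analytes. If the abnormality persists or worsens, monitoring continues until levels normalize or are near baseline. If such unplanned tests qualify as the last nonmissing observation up to Week 26, a later and possibly lower value can take the place of the planned Week 16 value for those patients in this analysis.

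**Working it through.** **1. Does any reading of the calendar give Week 26?** Inputs: the periods in SAP 5.1, the timing of Visit 801 in protocol 5.3.1, and the visit windows in the protocol's Schedule of Activities (±7 days at Visits 13 and 801, ±3 days at Visits 2 to 4).

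| Time point | Arithmetic | Week |
|---|---|---|
| End of treatment (Visit 13) | 16 | 16 |
| Visit 801 as scheduled | 16 + 4 | 20 |
| Visit 801 at the end of its window | 20 + 1 | 21 |
| Visits 13 and 801 both 7 days late | 16 + 1 + 4 + 1 | 22 |
| Whole study counted from screening | 1 + 2 + 16 + 4 | 23 |
| From screening, every window run late | 3 + 9/7 + 16 + 1 + 4 + 1 | 26.3 |

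Only the last row comes near 26. It counts from screening and stacks every late window, whereas the schedule counts weeks from the first active dose and the SAP equates Week 16 with Visit 13. On the trial's own scale, Week 26 is 26 − 16 = 10 weeks after treatment, 26 − 20 = 6 weeks after the scheduled last visit, and 26 − 22 = 4 weeks after the latest visit the windows allow.

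**2. The rules side by side.**

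| Place | Limit | Planned tests only? |
|---|---|---|
| SAP 6.12.3.4.2, first ANCOVA | Week 16 visit | Yes |
| SAP 6.12.3.4.2, last observation | Week 26 | Not stated |
| SAP 6.12.4, last observation | Week 16 | Yes |
| Table ITRO 6.2, continuous chemistry | Visits 5-13 | Yes, with early discontinuation visits |
| Protocol 10.3.1 | Planned treatment period | Not stated |

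The last-observation sentence for liver enzymes is the only one with a limit beyond the treatment period.

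**3. What a literal reading would let in.** Week 16 is day 16 × 7 = 112 and Week 26 is day 26 × 7 = 182. A repeat comes 3 to 5 days after the elevated result; Visit 13 may fall 7 days either side of day 112.

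| Visit 13 on day | Repeat on days | By day 112? | By day 182? |
|---|---|---|---|
| 105 | 108-110 | Yes | Yes |
| 112 | 115-117 | No | Yes |
| 119 | 122-124 | No | Yes |

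The Week 26 limit admits the repeat in every row. A Week 16 limit alone still admits it when Visit 13 is early, so the restriction to planned tests is needed as well. With both in place, no repeat can displace the planned value.

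**4. Which results could change.** Only the supplementary ANCOVA. The first ANCOVA uses the planned Week 16 test. The elevation tables in SAP 6.12.3.4.3 use the maximum in the treatment period, so a lower repeat cannot overwrite a higher value. The profiles and listing there are triggered by any ALT or AST of at least 3 times, or total bilirubin of at least 2 times, the upper limit during treatment.

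**5. Size.** The documents give no expected number of patients with elevations, no enzyme standard deviation and no expected fall on retest. The effect on the supplementary ANCOVA therefore cannot be sized from them.

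**The case against.** The strongest reply is that Week 26 is an evident slip and that other text settles the matter. Liver enzymes belong to the chemistry panel (protocol Appendix 2), Table ITRO 6.2 fixes continuous chemistry to planned tests at Visits 5-13, and SAP 6.12.4 removes liver enzymes from its own analyses, not from that table. Where the SAP wants unplanned tests it says so, in 6.12.3.4.3. Silence in 6.12.3.4.2 is not permission. On that reading displacement is nil.

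Much of this stands, and it is why the point is minor. It does not make the sentence right. SAP 6.12.4 sends the reader to 6.12.3.4.2, which makes the Week 26 sentence the more specific instruction. The same section says planned for its first analysis and drops the word for its second. It also already departs from Table ITRO 6.2 in wording on baseline, taking the last value before randomization where the table gives Visit 1. A programmer could not be sure that the table governs.

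A reader might infer that the rule removes a liver signal, or that off-drug values are the fault. The documents support neither. The primary liver ANCOVA, the maximum-value tables, the profiles and the listing all retain an elevated Week 16 value. Study insulin stops at that visit ("Patients will give their last bolus dose of study insulin (LY900014 or Humalog) at Visit 13 with the MMTT or at early discontinuation"), so a repeat after Visit 13 is off drug, but off-drug data are included by design: "All patient data, regardless of whether on IP, will be used for the above analyses related to hepatobiliary events". That sentence concerns drug status and says nothing on planned versus unplanned tests or on the time window.

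**Conclusion.** Wrong as written, and minor. The Week 26 cut-off corresponds to no scheduled time point and conflicts with SAP 6.12.4, Table ITRO 6.2 and protocol 10.3.1. That finding rests on the documents' own calendar and needs no assumption.

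The consequence is conditional. A repeat test can replace a planned Week 16 value only if the sentence is read literally, Table ITRO 6.2 is set aside and unplanned tests are admitted. Even then it affects one supplementary ANCOVA, and only patients with a later test. An AST elevation alone is not among the protocol's retest triggers. A figure for the shift in arm means would require invented enzyme values and patient counts, so none is offered.

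**What to change.** In the last-observation sentence of SAP 6.12.3.4.2, replace Week 26 with Week 16 and add to the bracket that only planned tests are used, including those at early discontinuation visits. Week 16 should mean the nominal Visit 13, as in Table ITRO 6.2, so that a Visit 13 falling late within its window still counts.

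Repeat and follow-up tests need no new rule; SAP 6.12.3.4.3 already says how they are handled. Its percentages cover weeks 0 to 16, so a repeat taken after Week 16 does not enter them.

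The cost is one phrase in the SAP. No data collection, sample size or other analysis changes.

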6.12.3.4.3. Treatment-Emergent Elevation of Liver Enzyme Lab Values

The percentages of patients with the following elevations in hepatic laboratory tests at any time during the treatment period (0 to 16 weeks) will be summarized between treatment groups:

- The percentages of patients with post-baseline ALT measurement ≥ 3 times (3X), 5 times (5X), and 10 times (10X) the Covance upper limit of normal (ULN) will be summarized for all patients with a post-baseline value by the following baseline categories: $\leq 1X$, $> 1X$ to $< 3X$, $\geq 3X$, missing.
- The percentages of patients with post-baseline AST measurement greater than or equal to 3 3X, 5X, and 10X the Covance ULN will be summarized for all patients with a post-baseline value by the following baseline categories: $\leq 1X$, $> 1X$ to $< 3X$, $\geq 3X$, missing.
- The percentages of patients with post-baseline total bilirubin measurement ≥ 2 times (2X) the Covance ULN will be summarized for all patients with a post-baseline value by the following baseline categories: $\leq 1X$, $> 1X$ to $< 2X$, $\geq 2X$, missing.

Baseline will be the maximum observation in the baseline period including the lead-in period. The maximum value will be the maximum value from the treatment period. Planned and unplanned tests will be included.

Graphical profiles of ALT, AST, total bilirubin, and ALP will be provided for patients with an ALT or AST $\geq 3X$ ULN or total bilirubin $\geq 2X$ ULN during the treatment period. A listing for these patients will also be provided, including the actual measurement of ALT, AST, ALP, and total bilirubin, the corresponding reference high limits, demographics, disposition, drug exposure and AEs. The review for these patients includes an assessment of the proximity of any ALT or AST elevation to any total bilirubin elevation, ALP levels, other potential causes, and the temporal association with events such as nausea, vomiting, anorexia, abdominal pain, or fatigue.

All patient data, regardless of whether on IP, will be used for the above analyses related to hepatobiliary events.

